All clinical Adverse Events (AEs), Serious Adverse Events (SAEs), Treatment Emergent Adverse Events (TEAEs), withdrawal due to AEs, electrocardiograms (ECGs), vital signs and safety laboratory data will be reviewed and summarized on an ongoing basis during the study to evaluate the safety of subjects.

The safety analysis set will include all subjects who have received at least one dose of IP. Safety data will be presented in tabular and/or graphical format and summarized descriptively, where appropriate. All safety endpoints will be listed and summarized in accordance with Pfizer Standards. Categorical outcomes (eg, AEs) will be summarized by subject counts and percentage. Continuous outcome (eg, blood pressure (BP), pulse rate, etc) will be summarized using N, mean, median, standard deviation, etc. Change from baseline in laboratory data, ECGs and vital signs will also be summarized. Subject listings will be produced for these safety endpoints accordingly.

SCHEDULE OF ACTIVITIES

The schedule of activities table provides an overview of the protocol visits and procedures. Refer to the [STUDY PROCEDURES](#) and [ASSESSMENTS](#) sections of the protocol for detailed information on each procedure and assessment required for compliance with the protocol.

The investigator may schedule visits (unplanned visits) in addition to those listed on the schedule of activities table, in order to conduct evaluations or assessments required to protect the well-being of the subject.

Protocol Activity	Screening	Treatment Period						Follow Up/End of Study		Early Withdrawal ^b
	1	2	3	4	5	6	7	8 ^s	9	
Visit Identifier		Week 0	Week 1	Week 2	Week 4	Week 6	Week 8	Week 10	Week 12	
Study Day	Days -35 to Day 0	Day 1 ^s	Day 8	Day 15	Day 29	Day 43	Day 57	Day 71	Day 85	
Visit Window		±2 Days based on Week 0/Day 1 visit								
Informed consent	X									
Inclusion/Exclusion Criteria	X	X								
Demographics and RA history	X									
Prior RA medications check ^c	X	X								
Smoking History	X									
Medical history and Non RA medications	X									
History of Alcohol and Drug Abuse	X									
Height ^v	X									
Weight ^v	X								X	X
Contraception Check ^f	X	X	X	X	X	X	X	X ^s	X	X
Vital Signs (pulse rate, blood pressure), temperature ^d	X	X	X	X	X	X	X		X	X
Complete Physical Examination ^e	X	X							X	X
Targeted Physical Examination ^e			X	X	X	X	X			
Rash assessment	X	X	X	X	X	X	X	X ^s	X	X
ECG (12 lead) ^f	X	X					X		X	X
Chest X-ray ^g	X									
Audiogram ^y	X						X			X

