Patient Assessment of Arthritis Pain (PAAP) VAS	X	X	X	X	X	X	X	X	X	X
Patient's Global Assessment (PtGA) of Arthritis VAS	X	X	X	X	X	X	X	X	X	X
Physician's Global Assessment (PhGA) of Arthritis ^a	X	X	X	X	X	X	X	X	X	X
Health Assessment Questionnaire – Disability Index (HAQ-DI)	X	X	X	X	X	X	X	X	X	X
Serious and Non-Serious Adverse Event Assessment	X	→	→	→	→	→	→	→	X	X
Concomitant Medication & Treatments		X	→	→	→	→	→	→	X	X
Discharge from the study									X	X

Abbreviations: → = ongoing/continuous event; CRP = C-Reactive Protein; DNA = deoxyribonucleic acid ; ECG = electrocardiogram; EOS = end of study; ESR = Erythrocyte Sedimentation Rate; FACS = fluorescence-activated cell sorting; FSH = follicle stimulating hormone; HAQ-DI = Health Assessment Questionnaire – Disability Index; HBcAb = hepatitis B core antibody; HBsAg = hepatitis B surface antigen; HBsAb= hepatitis B surface antibody;

HCVAb = hepatitis C antibody; HIV = human immunodeficiency virus; hsCRP = high-sensitivity C-reactive protein; IgA, IgG, IgM, IgE = Immunoglobulin of the A, G, M, E isotypes; IGRA = Interferon Gamma Release Assay; IP = investigational product; IP-10 = IFN-gamma-inducible protein 10; IRB = institutional review board; PK = pharmacokinetic; PAAP = Patient Assessment of Arthritis Pain; PtGA = patient's global assessment; PhGA = Physician's Global Assessment; PK=Pharmacokinetics; RNA = Ribonucleic Acid; VAS = Visual Analog Scale; WONCBP = women of non-childbearing potential.

- a. Visits should occur when scheduled, within the time window indicated in the column headings. The screening visit is up to 5 weeks prior to Visit 2. On all clinic visit days, PtGA and PAAP VAS measures and HAQ-DI questionnaires, should be performed prior to any other assessments. Vital signs, ECG and blood draws should be performed as specified in [Section 7](#). Assessments including joint counts, physician questionnaire, and pre-dose blood collections are to be performed prior to dosing unless otherwise stated. Physician's assessment should be performed without knowledge of patient reported VAS assessments. Additional unscheduled assessments should be performed as clinically indicated.

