- o. At the baseline visit, (Visit 2) the first dose of investigational product will be taken in the clinic. Additionally, at Weeks 1, 2, 4, 6 and 8 subjects should be given their dose for that day in the clinic. All other doses will be taken by the subject outside of the clinic.
- p. Subject diary dispensed and/or collected. Subject diary, study compliance and investigational product administration entries are reviewed. See [Section 5.3](#).

- q. If not collected on the designated collection day, collect at the next available time point when biospecimens are being collected in conjunction with a subject visit.
- r. Except for women of non-child bearing potential. See [Section 4.3.1](#) and [Section 7.2.4](#).
- s. Telephone follow up. Adverse Event and rash assessments (if needed) will be conducted verbally over the phone and if needed subject will be asked to come in for AE assessment. Use of contraception will be confirmed and concomitant medication check will be done over the phone with the subject.
- t. To confirm postmenopausal status (if applicable).
- u. In addition to time points specified, a plasma sample for viral surveillance sample may also be taken at the time of an adverse event. See [Section 7.2.10](#) for details.
- v. Height and Weight will be measured without shoes.
- w. At the time of the visit, a blood sample will be collected for PK analysis. As with all PK assessments, date and time of last dose and date and time of sample collection should be captured and reported.
- x. Baseline Visit.
- y. Audiogram testing at screening must be completed and results available by the baseline visit (Visit 2) and audiogram testing at Week 8 (Visit 7) must be completed and results available by the Week 12 visit (Visit 9). For subjects that terminate early from the study, if possible, efforts must be made to complete the audiology testing and obtain the results. See [Section 7.2.12](#) for details.

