5. STUDY TREATMENTS

For the purposes of this study, and per International Conference on Harmonisation (ICH) guidelines, investigational product is defined as a pharmaceutical form of an active ingredient or placebo being tested or used as a reference/comparator in a clinical trial, including a product with a marketing authorization when used or assembled (formulated or packaged) in a way different from the approved form, or when used for an unapproved indication, or when used to gain further information about an approved use (ICH E6 1.33).

For this study, the investigational product is PF-06651600. Investigational product will be administered only to subjects who have provided informed consent. Once a subject's participation in the study has ended, investigational product will no longer be supplied to the subject by the investigative site and/or sponsor.

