5.4.2. Preparation and Dispensing

The investigational product will be dispensed using an IRT drug management system at each visit from Week 0 through Week 8. Each dispensing visit will provide sufficient investigational product to complete dosing until the next scheduled dispensing visit. Visit dates are calculated such that visit windows are not cumulative and are anchored on Day 0.

Investigational product should be dispensed by an appropriately qualified and experienced member of the study staff (eg, physician, nurse, physician's assistant, practitioner, or pharmacist) as allowed by local, state, and institutional guidance. Only qualified personnel who are familiar with procedures that minimize undue exposure to their person and to the environment should undertake the preparation, handling, and safe disposal of agents.

The subject should be instructed to maintain the product in the blister cards provided throughout the course of dosing and return the blister cards to the site at the next study visit.

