5.5. Administration

Subjects will receive PF-06651600 tablets and matching placebo for oral administration in blister packs. Subjects will be dispensed blister cards and given clear dosing instructions.

Investigational product tablets will be administered to the subject in the clinic on the morning of clinic visits and all other dosing will be performed by the subject outside of the clinic. Subjects will record their study drug dosing information within a Subject Dosing Diary which should be brought to each clinic visit.

Sites will be trained on how subjects should take tablets at home through the study or IP manual and/or other vehicle(s). Sites are responsible for communicating this information to the subject.

If a dose is missed and the interval to the next dose is less than 6 hours, the missed dose should not be administered. At the baseline visit, (Visit 2) the first dose of investigational product will be taken in the clinic. Additionally, at Weeks 1, 2, 4, 6 and 8 subjects should take their dose for that day in the clinic. All other doses will be taken by the subject outside of the clinic.

The investigational product may be administered with or without food. Subjects will swallow the investigational product whole, and will not manipulate or chew the investigational product prior to swallowing with a glass of water.

Subjects who experience AEs that require treatment may have their study drug temporarily discontinued during treatment at the investigator's discretion. Subjects interrupting investigational product for more than 5 days are to be discussed with the medical monitor for possible discontinuation from the study.

Temporary discontinuation of study drug should be recorded in the CRF.

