14. SPONSOR DISCONTINUATION CRITERIA

Premature termination of this study may occur because of a regulatory authority decision, change in opinion of the IRB/EC, or investigational product safety problems, or at the discretion of Pfizer. In addition, Pfizer retains the right to discontinue development of PF-06651600 at any time. If a study is prematurely terminated, Pfizer will promptly notify the investigator. After notification, the investigator must contact all participating subjects and the hospital pharmacy (if applicable) within 1 month. As directed by Pfizer, all study materials must be collected and all CRFs completed to the greatest extent possible.

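### Section 14 allows sites up to one month to contact subjects after early termination, even for safety, which is longer than any interval between dispensing visits

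*Protocol*

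**What the plan says.** Protocol Section 14 allows early termination for a regulatory decision, a change in IRB/EC opinion, product safety problems, or at the sponsor's discretion. The sponsor is to notify the investigator promptly. The next step has one limit, whatever the reason: "After notification, the investigator must contact all participating subjects and the hospital pharmacy (if applicable) within 1 month". Section 14 then has materials collected as the sponsor directs. It gives no shorter time for a safety stop and no instruction about dosing.

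Supply and dosing are described elsewhere in the Protocol:

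- Section 5.4.2: "Each dispensing visit will provide sufficient investigational product to complete dosing until the next scheduled dispensing visit", and "Visit dates are calculated such that visit windows are not cumulative and are anchored on Day 0".
- Section 5.5: doses are taken in the clinic on visit mornings, and "all other dosing will be performed by the subject outside of the clinic".
- Schedule of Activities: clinic visits in the treatment period fall on Days 1, 8, 15, 29, 43 and 57, with a window of plus or minus "2 Days based on Week 0/Day 1 visit". Footnote o adds that "at Weeks 1, 2, 4, 6 and 8 subjects should be given their dose for that day in the clinic".
- Section 5: once a subject's participation has ended, "investigational product will no longer be supplied to the subject by the investigative site and/or sponsor".

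**The concern.** A contact deadline protects a subject on drug only if it can fall before the drug in hand runs out. Here the limit is 28 to 31 days, while the supply lasts one or two weeks. For subjects holding drug, the limit never forces a contact earlier than a visit already planned.

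At stake is avoidable exposure to a product just stopped for safety. The case is worth covering in this trial. It is the first study of the drug in rheumatoid arthritis (Section 1.6.1), the drug is under suspicion of teratogenicity from nonclinical findings (Section 4.3.1), and there is no data monitoring committee (Section 9.6). The Protocol is also much quicker elsewhere. Serious adverse events go to the sponsor within 24 hours (Section 8.1), and subjects with possible drug-induced liver injury should return preferably within 48 hours (Section 8.4.2).

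**Working it through.** The plan states no figure for doses in hand, so there is nothing to reproduce first. This is a direct count.

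**Inputs.** Once-daily dosing for 8 weeks (Section 3); clinic doses on Days 1, 8, 15, 29, 43 and 57 (Schedule of Activities); supply to the next dispensing visit (Section 5.4.2); non-cumulative 2-day windows; 30 active and 20 placebo completers (Section 9.1). Subjects in screening are left out: "The screening visit is up to 5 weeks prior to Visit 2", so screening can outlast a month, but they hold no drug.

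**Doses in hand.** Home doses per interval = gap − 1, because the visit-day dose is taken in the clinic. For the longest gap, the Day 1 visit is fixed and each later visit can move 2 days either way.

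| Interval | Scheduled gap (days) | Home doses | Doses in hand, summed over days | Longest gap with windows (days) |
|---|---|---|---|---|
| Day 1–8 | 7 | 6 | 6+5+…+0 = 21 | 9 |
| Day 8–15 | 7 | 6 | 21 | 11 |
| Day 15–29 | 14 | 13 | 13+12+…+0 = 91 | 18 |
| Day 29–43 | 14 | 13 | 91 | 18 |
| Day 43–57 | 14 | 13 | 91 | 18 |
| Total | 56 | 51 | 315 | |

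- **Limit against gaps.** One month, taken as 28, 30 or 31 days, exceeds every scheduled gap and the longest windowed gap of 18 days.
- **Maximum in hand.** On schedule, 13 doses, which is 13/57 = 23% of the 57 planned doses (Days 1 to 57). At the window extremes 18 − 1 = 17, but only if the pack holds that many; pack size is not stated.
- **Mean in hand.** With termination equally likely on each of Days 1 to 56: (2 × 21 + 3 × 91)/56 = 315/56 = 5.6. Counting before instead of after that day's dose gives the same mean.
- **Active doses, averaged over both arms.** 5.625 × 30/50 = 3.4.

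**With contact within 48 hours.** At most 2 further doses are taken. Capping each day's count at 2 gives 11 for a 7-day interval and 25 for a 14-day interval.

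- Mean further doses: (2 × 11 + 3 × 25)/56 = 97/56 = 1.7.
- Largest saving: 13 − 2 = 11 on schedule; 17 − 2 = 15 at the window extremes, with the same pack-size condition.
- Worst-case mean saving: (315 − 97)/56 = 3.9; in active doses over both arms, 3.89 × 0.6 = 2.3.
- Days on which a subject holds more than 2 home doses: 2 × 4 + 3 × 11 = 41 of 56 (73%). Only on these days could the shorter limit matter, and then only if the site would otherwise have called later than 48 hours.

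**Other sections that might supply a shorter time.**

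- Section 5 ends new supply; it does not address tablets already at home.
- Section 5.7 ties return of blister cards to visits and the end of the trial.
- Section 6.4 and Appendix 5 give power to withdraw subjects. The one-week follow-up visit in Section 6.4 is timed from the last dose, so it sets no time for telling the subject to stop.
- Section 12.1 lets a change needed to remove an immediate hazard precede IRB/EC approval. Section 12.4 has the investigator inform the sponsor of urgent safety measures taken.
- In Section 14 itself, the promptness requirement covers only sponsor to investigator, and the sponsor's direction covers materials and case report forms.

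None sets a time for telling subjects of a trial-level stop.

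**The case against.** The strongest reply is that the month is an outer limit for close-out, covering all subjects, the pharmacy and every reason for stopping. It sits between prompt notice to the site and collection of materials as the sponsor directs, so the sponsor's notice can carry whatever urgency a safety stop needs. Section 6.4 lets the sponsor withdraw subjects for safety at any time, and nothing confines this to one subject at a time. Section 12.2 binds the study to GCP and legal requirements. Exposure is also limited by dispensing only to the next visit, and about 40% of the doses counted are placebo.

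Much of this stands, and it limits the claim:

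- A reader might infer that the Protocol permits dosing to continue for a month after a safety stop. It does not. Nothing in Section 14 authorises continued dosing, and the supply would run out sooner.
- A reader might infer that a site could wait this long and still comply with all its obligations. The documents cannot show that. The statement holds for Section 14 alone, because the GCP text that also applies is not in them.
- A reader might take 3.9 doses as the expected saving. It is an upper bound on the on-schedule mean, because it assumes that without the change every site makes contact only after the pack is empty. The true saving is smaller and unknown.

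What the reply does not do is point to a stated time. Powers to act quickly exist, but the only deadline written for this step is too long to protect a subject holding drug.

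**Conclusion.** The concern holds as a minor safety point. For subjects holding drug, the single one-month limit cannot act before the home supply is used, and no other section supplies a shorter time. The sizes rest on on-schedule visits, full adherence, a termination day spread evenly over treatment, and the planned 30:20 completer split applying to subjects on treatment. The maximum of 13 doses needs neither the even spread nor the split; it still applies to an individual active-arm subject.

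The risk also needs three things together: a safety termination, a site that delays, and a sponsor notice that sets no urgency. That combination keeps the severity low. It is worth changing because the change is cheap, not because harm is likely. No endpoint, analysis or blinding is affected.

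**What to change.** Keep one month for administrative close-out and pharmacy contact. Add one sentence to Section 14:

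> If the study is terminated for a safety reason, the investigator must contact every subject still holding investigational product within 48 hours of notification (sooner where possible), instruct the subject to stop dosing and arrange return of the remaining product.

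The 48-hour figure is a judgement; it matches the time already used for possible liver injury in Section 8.4.2. The cost is one sentence in an amendment. The contacts are already required, and telephone follow-up is already used at Week 10. The downside is that sites must make the same contacts sooner, possibly out of hours, when the reason is safety.

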15. PUBLICATION OF STUDY RESULTS

15.1. Communication of Results by Pfizer

Pfizer fulfills its commitment to publicly disclose clinical trial results through posting the results of studies on www.clinicaltrials.gov (ClinicalTrials.gov), the European Clinical Trials Database (EudraCT), and/or www.pfizer.com, and other public registries in accordance with applicable local laws/regulations.

In all cases, study results are reported by Pfizer in an objective, accurate, balanced, and complete manner and are reported regardless of the outcome of the study or the country in which the study was conducted.

www.clinicaltrials.gov

Pfizer posts clinical trial US Basic Results on www.clinicaltrials.gov for Pfizer-sponsored interventional studies (conducted in subjects) that evaluate the safety and/or efficacy of a Pfizer product, regardless of the geographical location in which the study is conducted. US Basic Results are submitted for posting within 1 year of the primary completion date (PCD) for studies in adult populations or within 6 months of the PCD for studies in pediatric populations.

PCD is defined as the date that the final subject was examined or received an intervention for the purposes of final collection of data for the primary outcome, whether the clinical study concluded according to the prespecified protocol or was terminated.

[EudraCT](#)

Pfizer posts European Union (EU) Basic Results on EudraCT for all Pfizer-sponsored interventional studies that are in scope of EU requirements. EU Basic Results are submitted for posting within 1 year of the PCD for studies in adult populations or within 6 months of the PCD for studies in pediatric populations.

www.pfizer.com

Pfizer posts Public Disclosure Synopses (clinical study report synopses in which any data that could be used to identify individual subjects has been removed) on www.pfizer.com for Pfizer-sponsored interventional studies at the same time the US Basic Results document is posted to www.clinicaltrials.gov.

15.2. Publications by Investigators

Pfizer supports the exercise of academic freedom and has no objection to publication by the principal investigator (PI) of the results of the study based on information collected or generated by the PI, whether or not the results are favorable to the Pfizer product. However, to ensure against inadvertent disclosure of confidential information or unprotected inventions, the investigator will provide Pfizer an opportunity to review any proposed publication or other type of disclosure of the results of the study (collectively, “publication”) before it is submitted or otherwise disclosed.

The investigator will provide any publication to Pfizer at least 30 days before it is submitted for publication or otherwise disclosed. If any patent action is required to protect intellectual property rights, the investigator agrees to delay the disclosure for a period not to exceed an additional 60 days.

The investigator will, on request, remove any previously undisclosed confidential information before disclosure, except for any study- or Pfizer product-related information necessary to the appropriate scientific presentation or understanding of the study results.

If the study is part of a multicenter study, the investigator agrees that the first publication is to be a joint publication covering all investigator sites, and that any subsequent publications by the PI will reference that primary publication. However, if a joint manuscript has not been submitted for publication within 12 months of completion or termination of the study at all participating sites, the investigator is free to publish separately, subject to the other requirements of this section.

For all publications relating to the study, the institution will comply with recognized ethical standards concerning publications and authorship, including Section II - “Ethical Considerations in the Conduct and Reporting of Research” of the Uniform Requirements for Manuscripts Submitted to Biomedical Journals, <http://www.icmje.org/index.html#authorship>, established by the International Committee of Medical Journal Editors.

Publication of study results is also provided for in the CSA between Pfizer and the institution. In this section entitled Publications by investigators, the defined terms shall have the meanings given to them in the CSA.

If there is any conflict between the CSA and any attachments to it, the terms of the CSA control. If there is any conflict between this protocol and the CSA, this protocol will control as to any issue regarding treatment of study subjects, and the CSA will control as to all other issues.

